1. KSS-PATIENT CATEGORY			
 Unilateral or bilateral (opposite knee successfully replaced)  Unilateral, Other Knee Symptomatic  Multiple Arthritis or Medical Infirmity (specify) 			
2. KSS-PAIN/MOTION SCORE			
Pain:  None  Moderate occasional  Mild or occasional  Moderate continual  Mild or occasional, stairs only  Severe  Mild or occasional, walking and stairs		ACTIVE Range of Motion: Neutral Zero Method:  PASSIVE Range of Motion: Neutral Zero Method: 	
Stability (amount of motion): Anteroposterior (Check one) Mediolateral (Check one)  < 5mm  < 5°  5 - 10 mm  5° - 9°  > 10mm  10° - 15°  > 15°		Alignment (Check one):  Valgus: (please specify degrees)   Varus: (please specify degrees)   Pain motion score not done	
3. KSS-FUNCTION SCORE			
Walking aids  None  Unlimited  Cane  > 10 blocks / > 1000m, > 3280 feet  Two canes / one crutch  5-10 blocks / 500m - 1000m, 1640-3280 feet  Crutches or walker, cannot walk / wheelchair  < 5 blocks / < 500m, < 1640 feet  Housebound		Walking  Normal up & down  Normal up; down with rail  Up & down with rail  Up with rail; unable down  Unable	
 Function motion score not done			
Investigator Name (Print)			INITIAL/DATE
Investigator Signature			Monitored: /
Date			Receipt: /
			Entry: /
			Verification: /

Stryker® Simplex HV Retrospective Study				
Page 1 of 2	OKS	Patient ID	8 0	Study#, Center#, Subject#, Side (UR)
GENERAL INFORMATION				
Patient code (Use AA, BB,...AB)		Date of examination	 D D	 M M M Y Y Y
Pre-op visit 	Follow-up at  12-24 months (+2 months) post study surgery  5 years (\pm 3 months) post study surgery, specify	 years  months		
OKS SCORE				
1. How would you describe the pain you usually have in your knee?				
 None	 Very mild	 Mild	 Moderate	 Severe
2. Have you had any trouble washing and drying yourself (all over) because of your knee?				
 No trouble at all	 Very little trouble	 Moderate trouble	 Extreme difficulty	 Impossible to do
3. Have you had any trouble getting in and out of the car or using public transport because of your knee? (With or without a stick)				
 No trouble at all	 Very little trouble	 Moderate trouble	 Extreme difficulty	 Impossible to do
4. For how long are you able to walk before the pain in your knee becomes severe? (With or without a stick)				
 No pain > 60 min	 16 - 60 minutes	 5 - 15 minutes	 Around the house only	 Not at all - severe on walking
5. After a meal (sat at a table), how painful has it been for you to stand up from a chair because of your knee?				
 Not at all painful	 Slightly painful	 Moderately pain	 Very painful	 Unbearable
6. Have you been limping when walking, because of your knee?				
 Rarely / Never	 Sometimes or just at first	 Often, not just at first	 Most of the time	 All of the time
7. Could you kneel down and get up again afterwards?				
 Yes, easily	 With little difficulty	 With moderate difficulty	 With extreme difficulty	 No, impossible

Please continue on page 2 of 2

[figure not shown]
[figure not shown]
Stryker® Simplex HV Retrospective Study																																																											
Page 2 of 2	OKS	Patient ID	8 0	Study#	Center#	Subject#	Side (L/R)																																																				
GENERAL INFORMATION																																																											
Patient code (Use AA, BB,...AB)	Date of examination	
 
 D D	M M M	Y Y Y Y	
 
 years	months		
 
								D D	M M M	Y Y Y Y	years	months																																													
D D	M M M	Y Y Y Y																																																									
years	months																																																										
Pre-op visit 	Follow-up at  12-24 months (+2 months) post study surgery																																																										
	 5 years (\pm 3 months) post study surgery, specify																																																										
OKS SCORE																																																											

8. Are you troubled by pain in your knee at night in bed?
 
 
 	
 
 Not at all	Only one or two nights	Some nights	Most nights	Every night	
 
 
9. How much has pain from your knee interfered with your usual work? (including housework)
 
 
 	
 
 Not at all	A little bit	Moderately	Greatly	Totally	
 
 
10. Have you felt that your knee might suddenly give away or let you down?
 
 
 	
 
 Rarely / Never	Sometimes or just at first	Often, not at first	Most of the time	All the time	
 
 
11. Could you do household shopping on your own?
 
 
 	
 
 Yes, easily	With little difficulty	With moderate difficulty	With extreme difficulty	No, impossible	
 
 
12. Could you walk down a flight of stairs?
 
 
 	
 
 Yes, easily	With little difficulty	With moderate difficulty	With extreme difficulty	No, impossible	
 
															Not at all	Only one or two nights	Some nights	Most nights	Every night		Not at all	A little bit	Moderately	Greatly	Totally		Rarely / Never	Sometimes or just at first	Often, not at first	Most of the time	All the time		Yes, easily	With little difficulty	With moderate difficulty	With extreme difficulty	No, impossible		Yes, easily	With little difficulty	With moderate difficulty	With extreme difficulty	No, impossible																
																																																											
Not at all	Only one or two nights	Some nights	Most nights	Every night																																																							
																																																											
Not at all	A little bit	Moderately	Greatly	Totally																																																							
																																																											
Rarely / Never	Sometimes or just at first	Often, not at first	Most of the time	All the time																																																							
																																																											
Yes, easily	With little difficulty	With moderate difficulty	With extreme difficulty	No, impossible																																																							
																																																											
Yes, easily	With little difficulty	With moderate difficulty	With extreme difficulty	No, impossible																																																							
Investigator Name (Print)					For Stryker Use Only		INITIAL/DATE:																																																				
Investigator Signature					Stamp Date Received:		Monitored: _____ / _____																																																				
Date	
 
 D D	M M M	Y Y Y Y	
 
				D D	M M M	Y Y Y Y			Receipt: _____ / _____																																																	
D D	M M M	Y Y Y Y																																																									
							Entry: _____ / _____																																																				
							Verification: _____ / _____																																																				

Simplex HV Retrospective Study			
Page 1 of 2	INTRA-OPERATIVE	Patient ID	8 0 Study# Cont# Subject# Side (L/R)
GENERAL INFORMATION			
Patient code (Use AA, BB,...AB)		Surgery date	 DD MM YY
SURGICAL DETAILS			
Type of Anesthesia (check all that apply)		Anesthesia Class ASA (check one)	
 Anesthesia:	 General  Epidural  Spinal  Femoral Block	 ASA class:	 1 excellent  2 good-moderate  3 fair  4 poor
 unknown		 unknown	
Systemic Prophylactic Therapy		Surgical Approach (check one)	
 Antibiotic	 Anticoagulant	 unknown	 Medial parapatellar  Lateral parapatellar  Other
Surgeon Initials			
Time		Blood Loss	
Skin to skin	 minutes	 ml	
Tourniquet	 no  yes  unknown	 unknown	
SIMPLEX HV DETAILS			
Cement Storing Temperature		Operating Room Temperature	
Standard cement storing temperature between 0 °C/32 °F and +25 °C/77 °F		 Hospital standard select unit	 °C /  °F
 yes  unknown		 Temperature less than 21 °C/70 °F  Temperature higher than 21 °C/70 °F  Temperature unknown	
Cement Type		Cement Preparation	
 Simplex HV non-medicated  Simplex HV Gentamycin		 Hand mixed  Vacuum mixed  unknown	
Cement Use			
Cementless tibial component is exclusion criterion			
 Femoral component  Tibial component			

continue on page 2 of 2

Stryker®		Simplex HV Retrospective Study						
Page 2 of 2	INTRA-OPERATIVE	Patient ID		8 0	Study#	Control#	Subject#	Side (L/R)
GENERAL INFORMATION								
Patient code (Use AA, BB,...AB)			Surgery date		 D D /  M M M /  Y Y Y Y			
TRIATHLON TOTAL KNEE REPLACEMENT DETAILS								
Femoral Component								
 PS Femoral Component cemented 5515-F-X01 left  PS Femoral Component cemented 5515-F-X02 right  CR Femoral Component cemented 5510-F-X01 left  CR Femoral Component cemented 5510-F-X02 right  Size X:  1  2  3  4  5  6  7  8								
Tibial Component								
 Primary Tibial Baseplate cemented 5520-B-X00  Size X:  1  2  3  4  5  6  7  8  Primary MIS Baseplate cemented 5520-M-X00  Size X:  1  2  3  4  5  6  7  8								
Tibial Insert								
Insert	 CR (5530)	 CS (5531)	 PS (5532)					
Material	 X3 (G)	 Conventional (P)						
Height mm	 9	 11	 13	 16	 19	 22*	 25*	*CS and PS only
Patella								
Replaced	 No	 Yes, specify						
	Shape		 Symmetric (5550)	 Asymmetric (5551)				
	Material		 X3 (G)	 Conventional (L)				
INTRA-OP ADVERSE EVENT / DEVICE DEFICIENCY								
 No  Yes, complete complication-report								
Investigator Name (Print)					For Stryker Use Only		INITIAL/DATE	
Investigator Signature					Stamp Date Received:		Monitored:	/
Date	 D D /  M M M /  Y Y Y Y						Receipt:	/
							Entry:	/
							Verification:	/

Stryker® Simplex HV Retrospective Study										
Page 1 of 1	Follow-up			Patient ID						
				8 0						
				Study#	Contor#	Subject#	Side (L/R)			
GENERAL INFORMATION										
Patient code (Use AA, BB,...AB)	Date of examination									
	D	D	M	M	M	Y	Y	Y	Y	
	Follow-up at:			 12-24 months (+2 months) post study surgery  5 years (\pm 3 months) post study surgery, specify						
4. X-RAY COLLECTION (A/P and lateral view)										
Date of x-ray				 x-ray not available						
	D	D	M	M	M	Y	Y	Y	Y	
5. ANY OTHER SCHEDULED HIP/KNEE JOINT REPLACEMENT SINCE STUDY SURGERY										
 No	 Yes, specify			 Contralateral knee, surgery date						
	D	D	M	M	M	Y	Y	Y	Y	
	 Ipsilateral hip, surgery date			 Contralateral hip, surgery date						
	D	D	M	M	M	Y	Y	Y	Y	
6. POST-OP SERIOUS ADVERSE EVENT/DEVICE DEFICIENCY										
 No	 Yes, due to aseptic loosening*			 Yes, due to other reason*						
*If yes, please specify in Adverse Event Form										
Investigator Name (Print)					For Stryker Use Only					
Investigator Signature					Stamp Date Received:					
Date										
	D	D	M	M	M	Y	Y	Y	Y	
INITIAL/DATE										
					Monitored: _____ / _____					
					Receipt: _____ / _____					
					Entry: _____ / _____					
					Verification: _____ / _____					

Stryker® Simplex HV Retrospective Study			
Page 1 of 1	Knee Society Score	Patient ID 8 0	
		Study#	Center#
		Subject#	Side (L/R)
GENERAL INFORMATION			
Patient code (Use AA, BB,...AB)		Date of examination 	
Pre-op visit 	Follow-up at  12-24 months (+2 months) post study surgery  5 years (± 3 months) post study surgery, specify 		

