5.4 Post-operative Data Collection

Data collection at 24 months (+ 2 months) postoperatively and optional at 5 years postoperative.

- Knee Society Score (KSS)
- Oxford Knee Score (OKS)
- X-ray collection for independent analysis
 - A/P view
 - Lateral view
- Elective surgery since study surgery
- Post-operative Adverse event or device deficiency

6 Adverse Events

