6.1 Reporting of Adverse Events

The AE reporting requirements for this study are as follows:

- All AEs that meet the definition of serious
- All AEs related to the operative site, regardless of seriousness or time of occurrence

On retrospective review of postoperative data, investigators and study coordinators (SCs) will search the subject's hospital files as to whether they have seen a doctor for any reason, been hospitalized for any reason or have a current impediment to their function.

If it is determined upon this further investigation that a protocol-defined AE has occurred, the SC will be responsible to complete an AE CRF. If the event is related or uncertain related to the Triathlon TKA or to Simplex HV, the investigator will verify if the event has been reported to Stryker at time point of occurrence or will report at time point of data review at the latest. The event shall be reported to Stryker and to the IRB/EC, as required.

The following decision tree facilitates identification of AEs for which reporting is required under this study protocol:

[figure not shown]
Figure 1. Adverse Event Decision Tree

Figure 1 Adverse event decision tree

General Retrospective Review Findings

At screening for inclusion into the study, any clinically significant abnormality should be recorded as a preexisting condition and reported on the Demographics CRF. From the time of surgery forward, any new clinically significant findings or abnormalities that meet the definition of a protocol defined AE must also be recorded and documented as an AE until the end of the observation period or maximum at the five years follow-up.

Adverse Event Reporting Period

The study period during which AEs must be reported is defined as the period from the surgery to the last protocol specified follow-up.

During retrospective review of the subject's hospital files, information on protocol defined AEs shall be recorded in the AE CRF. The clinical course of each event should be followed until resolution or until it is determined at the end of the study that the AE will not resolve.

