6.2 General Adverse Event Definitions

Following is a list of general AE definitions. For the purposes of this study, only SAEs, excluding elective procedures, as well as all AEs related to the operative site should be reported.

Adverse Event

An **AE** is any untoward medical occurrence, in a clinical investigation subject which changes the medical baseline of the subject, users or other persons. An AE can be an unfavorable and unintended sign, symptom or disease, whether or not related to the study device (AEs may also be referred to as complications). See Section 6.1, Reporting of Adverse Events, for the AE reporting requirements for this study.

NOTE 1 This definition includes events related to the investigational medical device or the comparator.

NOTE 2 This definition includes events related to the procedures involved.

NOTE 3 For users or other persons, this definition is restricted to events related to investigational medical devices.

Anticipated Adverse Event

An **anticipated AE** is an AE, of which the nature, severity or degree of incidence is known and identified in applicable product labeling, published literature or the study protocol. The list of anticipated events is provided in Section 12, Risk/Benefit Assessment.

Serious Adverse Event

A **SAE** meets one or more of the following definitions:

- led to death,
- led to serious deterioration in the health of the subject, that either resulted in
- a life-threatening illness or injury, or
- a permanent impairment of a body structure or a body function, or
- in-patient or prolonged hospitalization, or
- medical or surgical intervention to prevent life-threatening illness or injury or permanent impairment to a body structure or a body function,
- led to foetal distress, foetal death or a congenital abnormality or birth defect

NOTE Planned hospitalization for a pre-existing condition, or a procedure required by the protocol, without serious deterioration in health, is not considered a serious adverse event

Adverse Device Effect

An **adverse device effect (ADE)** is a negative change in the subject's health that may have been caused by, or associated with, the use of the device.

Unanticipated Adverse Device Effect

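### Follow-up CRF item 6 asks only about serious adverse events and device deficiencies, while Sections 6.1 and 6.2 require every operative-site event, so non-serious ones may be missed

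*Combined protocol and SAP*

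**What the plan says.** Section 6.1 sets two reporting requirements: "All AEs that meet the definition of serious" and "All AEs related to the operative site, regardless of seriousness or time of occurrence". Section 6.2 restates the scope: "only SAEs, excluding elective procedures, as well as all AEs related to the operative site should be reported". Section 5.4 lists "Post-operative Adverse event or device deficiency" among the post-operative data, and Table 1 lists adverse events at the 24-month assessment. Neither mentions seriousness.

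The case report forms in Appendix B differ from each other. The Intra-operative form asks about "INTRA-OP ADVERSE EVENT / DEVICE DEFICIENCY". The Follow-up form, item 6, asks about "POST-OP SERIOUS ADVERSE EVENT/DEVICE DEFICIENCY". Its answers are 'No', yes for aseptic loosening, and yes for another reason. Both 'yes' answers carry the note "If yes, please specify in Adverse Event Form", and no other item on that form points to the Adverse Event Form.

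Complications are part of the secondary objective in the Synopsis. Section 9.2.2 plans frequencies and percentages for all protocol-defined adverse events.

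**The concern.** The form and the protocol ask different questions about the same period. A coordinator abstracting a chart with, say, a superficial wound problem that needed no admission can answer 'No' to item 6 and be correct against its heading. Nothing else on the form then leads to the Adverse Event Form, although Section 6.1 requires the event to be recorded.

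Any loss through this prompt goes one way, towards fewer recorded complications. It could also differ by site, according to whether staff work from the form or from Section 6.1. That matters for reading the tables, because Section 2.3 allows one site to contribute only non-medicated cement cases and another only gentamicin cases. A difference in capture between sites could then look like a difference between cements.

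**Working it through.** The plan states no adverse event rate, so there is no figure to reproduce. The first step is to compare the texts.

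| Place | Limited to serious events? | Operative-site events named? |
|---|---|---|
| Section 6.1 | No, for operative-site events | Yes |
| Section 6.2 | No, for operative-site events | Yes |
| Section 5.4 | No | Not mentioned |
| Intra-operative CRF prompt | No | Not mentioned |
| Follow-up CRF item 6 | Yes, plus device deficiencies | Not mentioned |
| Adverse Event Form | No; it has a non-serious option | Yes, as an event group |

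Only item 6 carries the restriction. The exposed events are those that are post-operative, related to the operative site and non-serious. Serious events are inside the heading, intra-operative events have their own unrestricted prompt, and device deficiencies are named in item 6.

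The second step is the possible size. Let p be the share of post-operative operative-site events that are non-serious, and m the share of those that go unrecorded because of the prompt. Then:

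- relative under-count = p × m
- recorded rate = true rate × (1 − p × m)

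Both p and m are assumptions: p from 50% to 75%, m from 0% to 50%.

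| p | m = 0 | m = 25% | m = 50% |
|---|---|---|---|
| 50% | 0% | 0.50 × 0.25 = 12.5% | 0.50 × 0.50 = 25% |
| 75% | 0% | 0.75 × 0.25 = 18.75% | 0.75 × 0.50 = 37.5% |

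For a sense of scale, assume a true post-operative operative-site rate of 20%. The recorded rate then lies between 20% (m = 0) and 0.20 × (1 − 0.375) = 12.5%. With the planned 100 cases per arm and one event per case, that is between 20 and 12.5 recorded events. At an assumed true rate of 10% the lower end is 0.10 × 0.625 = 6.25%, and at 30% it is 0.30 × 0.625 = 18.75%.

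The upper end reflects the choice to cap m at one half. The lower end, zero, is what follows if Section 6.1 is applied as written. The percentages refer to operative-site events only. Where the Section 9.2.2 total also contains serious events elsewhere in the body, its relative shortfall is smaller.

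**The case against.** The strongest reply is that item 6 does not control access to the Adverse Event Form. Section 6.1 tells staff to "search the subject's hospital files as to whether they have seen a doctor for any reason", and also to look for hospitalisation and functional impediment. It makes the coordinator complete an adverse event CRF whenever a protocol-defined event is found, whatever was ticked in item 6. The Adverse Event Form accepts non-serious and operative-site events and refers users to chapter 6 of the protocol. Section 10.1 has monitors compare all source documents with the CRFs, and Section 8.4 allows queries for omissions. Pain and range of motion are also scored on the KSS, and pain on the OKS, so those symptoms are not lost altogether.

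Much of this stands. It rules out saying that complications will be under-counted, and it is why the range must include zero. It does not remove the risk. A 'No' to item 6 is a valid answer to the question asked, so it shows no error or omission for a query to pick up. Section 8.3 describes monitors tracing each CRF data point to the chart, and an Adverse Event Form that was never opened supplies no data point. Full source review under Section 10.1 could still find the event, but it takes place only after the retrospective data have been documented, so a narrow reading could run through a site's whole series first. Scores on the KSS and OKS are not adverse event records and do not enter the Section 9.2.2 table.

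A reader might also infer that the primary result is compromised. The documents do not support that. Revision for aseptic loosening should meet the Section 6.2 definition of a serious event through surgical intervention or hospitalisation. Loosening has its own box in item 6, and revision for it has its own box on the Adverse Event Form.

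**Conclusion.** Item 6 contradicts Sections 6.1 and 6.2 and is narrower than Section 5.4 and the intra-operative prompt. As a result, non-serious post-operative operative-site events may be missed, possibly to different degrees by site, in the complications objective and the Section 9.2.2 table.

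The size cannot be derived from the documents. The relative under-count is 0% if the Section 6.1 route works fully, and 0% to 37.5% under the assumed inputs (50–75% of operative-site events non-serious, 0–50% of those missed).

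Two stronger readings are tempting. One sets the missed share at 25% or more and reports a minimum loss of 12.5%; that floor comes from the assumption, because nothing in the documents excludes full capture. The other expects a distorted comparison of the two cements. Differential capture by site is possible, but the plan only tabulates adverse events and sets no formal test or threshold for them, so the effect would be on how readers interpret the descriptive rates.

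The mismatch itself is certain; the resulting bias is only possible. It is worth correcting because the wrong instruction sits on the data collection form, and the primary endpoint is untouched.

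**What to change.** Retitle Follow-up CRF item 6 to: Post-op protocol-defined adverse event (any SAE, or any operative-site AE regardless of seriousness) / device deficiency. Keep the split between aseptic loosening and other reasons. Send sites a short notice, and re-check against Section 6.1 any form already completed with 'No'.

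This adds no reporting requirement; it makes the form ask for what Sections 6.1 and 6.2 already demand. The cost is a one-line CRF revision, the notice, the re-check of completed forms and slightly more Adverse Event Forms to abstract. The recorded complication rate may turn out less favourable.

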1. KSS-PATIENT CATEGORY			
 Unilateral or bilateral (opposite knee successfully replaced)  Unilateral, Other Knee Symptomatic  Multiple Arthritis or Medical Infirmity (specify) 			
2. KSS-PAIN/MOTION SCORE			
Pain:  None  Moderate occasional  Mild or occasional  Moderate continual  Mild or occasional, stairs only  Severe  Mild or occasional, walking and stairs		ACTIVE Range of Motion: Neutral Zero Method:  PASSIVE Range of Motion: Neutral Zero Method: 	
Stability (amount of motion): Anteroposterior (Check one) Mediolateral (Check one)  < 5mm  < 5°  5 - 10 mm  5° - 9°  > 10mm  10° - 15°  > 15°		Alignment (Check one):  Valgus: (please specify degrees)   Varus: (please specify degrees)   Pain motion score not done	
